## A. SPECIFIC AIMS

The aim of this study is to determine whether non-medical personnel, with no experience in ultrasound (US) use can effectively utilize the technology with remote guidance by expert assistance to assess for normal lung parenchyma among healthy volunteers.

#### **B. BACKGROUND AND SIGNIFICANCE**

US has become an increasingly utilized modality in the healthcare setting. Advances in US technology and a burgeoning field of research showing its efficacy has rendered US a crucial tool in such fields as emergency and critical care medicine. The portability and ease of use of US has led to its use in the fields of wilderness, polar and aerospace medicine as well. Portable US machines have been taken on mountaineering expeditions and launched to the International Space Station, at which times it has been used to diagnose high altitude pulmonary edema and monitor intracranial pressure among astronauts, respectively (Wimalasena et al 2013, Lerner et al 2016). Emergencies in remote environments such as space may necessitate the use of US by non-medical personnel, at which time the data gathered would be transmitted to medical professionals to be analyzed and upon which clinical decisions would be made. Small studies have shown the effectiveness of utilizing non-medically trained personnel in obtaining adequate US images for such evaluations as optic nerve sheath diameter and carotid artery dynamics (Martin et al 2012).

Extreme environments such as space, expose those in it to such risks as depressurization, which can lead to multiple lung pathologies such as pulmonary edema and/or pneumothorax (Galdamez et al 2017). In such circumstances, remotely guided ultrasound may prove crucial to quickly identifying such medical complications of extreme environments. This initial pilot study will determine the feasibility of using remotely guided ultrasound among non-medical personnel on healthy volunteers to identify normal lung parenchyma by identifying commonly used indicators of such (e.g. lung-sliding, a-lines). If the results of the study indicate that such operations are feasible, further investigations into whether non-medical personnel are able to identify lung pathologies among confirmed cases of such conditions as pulmonary edema or pneumothorax may be pursued.

#### C. RESEARCH DESIGN AND METHODS

#### 1. Rationale/overview

This study will assess the feasibility of remotely guided US use by individuals without ultrasound training to assess for normal lung parenchyma in healthy volunteers (patients) and amongst themselves. The untrained operators (operators) will perform US examinations of the lung under the guidance of a medical professional (expert) with experience in ultrasound technique. During the first portion of the study, the professional will guide the operator step by step on how to conduct an US exam of the 'patient's' lung. This simulation will be analogous to an untrained US operator assessing a potentially ill patient with the assistance of a remotely located physician.

The second portion of the study, during which time the participant will carry out an US exam on themselves, would be analogous to a lone patient in possession of US technology carrying out a self-examination under similar guidance of an expert. During both parts of the studye images will be saved and reviewed at a later time by an ultrasound expert to determine quality and clinical functionality in recognizing normal lung parenchyma. Images obtained by 'operators' will be compared against those obtained by US-trained clinicians (clinicians) captured from the same 'patient'. Real world examples of these scenarios would include an astronaut with respiratory distress after experiencing a rapid decompression event being evaluated by another healthy astronaut (or by themselves as in the second scenario) by US under the guidance of the flight surgeon at Mission Control.

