## 3. Study sample

A convenience sample of 20 healthy volunteers will be recruited from the Stony Brook undergraduate campus to participate as 'operators' in the study. 'Patients' will be recruited from a pool of standardized patient models who regularly participate in activities in the CSC. 10 US-trained clinicians will be recruited from SBU.

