## 5. Procedures

Volunteers will meet with study personnel in the CSC at SBU. Informed consent will be obtained from all groups ('operators', 'patients', 'clinicians'). A survey will be conducted to evaluate the subjects' prior experience in ultrasound. Subjects who qualify will continue to participate in the study.

The 'patient' will initially be evaluated by US by an expert and 'ideal' images will be captured and stored for later comparison against those obtained by 'operators'.

The 'operator' will be given an smart phone/table with video communication function and will be connected with the US 'expert', who will be located in a different room, physically and audibly out of range. For the first portion of the study, the 'expert' will instruct the 'operator' on how to conduct an US exam limited to the lung. Using the two-way video and audio communication through the video communication application, the expert will guide to the operator on how to utilize the US machine, where to place the probe, and how to capture and save images. The 'patient' will be instructed not to assist the 'operator' in any way. For the second portion of the study, the 'operator' will utilize the US machine to conduct a similarly limited lung exam on themselves, again with the assistance of the 'expert' but no other study personnel.

Finally, the 'clinicians' will carry out similarly limited lung exams on the 'patient', first without instruction from the 'expert' and then again under similar guidance as the previous portions of the study.

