## D. STATISTICAL ANALYSIS PLAN

'Final Scores' determined from the score sheets will be compared between the 'operators' and 'clinicians'.

Mean scores of the two groups will be reported, with their respective standard deviations. Student's T-Test will be carried out to assess difference between the two groups. All hypothesis testing will be carried out using two-sided 5% significance level.

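### The comparator is defined as clinician images of the same 'patient', but the allocation of 'patients' is not specified and the unpaired t-test ignores the match

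*Combined protocol and SAP*

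**What the plan says.** All places are in the combined protocol and SAP.

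- **C.1 Rationale/overview** defines the comparator: "Images obtained by 'operators' will be compared against those obtained by US-trained clinicians (clinicians) captured from the same 'patient".
- **C.3 Study sample** fixes the two scanning groups: "A convenience sample of 20 healthy volunteers will be recruited from the Stony Brook undergraduate campus to participate as 'operators' in the study" and "10 US-trained clinicians will be recruited from SBU". On the people scanned it says: "Patients' will be recruited from a pool of standardized patient models who regularly participate in activities in the CSC". It gives neither their number nor an allocation rule.
- **C.5 Procedures** has each clinician scan twice: "Finally, the 'clinicians' will carry out similarly limited lung exams on the 'patient', first without instruction from the 'expert' and then again", the second time under guidance. In the second portion, "the 'operator' will utilize the US machine to conduct a similarly limited lung exam on themselves".
- **C.5** also has an expert make reference images of each 'patient': "The 'patient' will initially be evaluated by US by an expert and 'ideal' images will be captured and stored for later comparison". Section D does not use them.
- **D. Statistical Analysis Plan** compares Final Scores between operators and clinicians: "Student's T-Test will be carried out to assess difference between the two groups". It mentions no pairing, blocking or patient term, and does not say which clinician exam enters.

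**The concern.** Several scorecard items, such as rib shadowing, visible A-lines and correct depth, plausibly depend on the body scanned as well as on the person scanning. A same-'patient' comparator is the design's control for that. It works only if the scans are scheduled to keep the match and the analysis uses it. The plan writes down neither step.

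What is at stake depends on the layout that results. If each 'patient' is scanned by both groups in the same proportion, patient differences cancel from the contrast, but the unpaired test still counts them as noise and gives up power. If the groups share the 'patients' unevenly, part of the observed difference is patient difficulty, and the test's standard error does not allow for it. With 20 and 10 exams, a few easy or hard models can move a group mean.

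**Working it through.** **Plan's own figure.** There is none to reproduce: the document gives no power, effect size, SD or sample-size derivation.

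**Inputs from the document.** 20 operators and 10 clinicians (C.3); two-sided 5% level and Student's t-test (D).

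**Assumptions, not in the document.** One 'patient' exam per person; normally distributed scores with total SD 1; a share ρ of score variance due to the patient, varied from 0 to 0.5; and the patient layouts below.

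**Model.** Score = group mean + patient effect (variance ρ) + residual (variance 1 − ρ). With no patient effect, the variance of the difference in means is 1/20 + 1/10 = 0.15, so its SD is 0.387.

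**Layout A: match kept and balanced** (10 'patients', each with 2 operators and 1 clinician).
- Each patient has weight 2/20 = 1/10 in the operator mean and 1/10 in the clinician mean, so patient effects cancel and there is no bias.
- True variance of the difference: 0.15 × (1 − ρ), which is 0.12 at ρ = 0.2 (SD 0.346) and 0.075 at ρ = 0.5 (SD 0.274).
- The pooled t-test still works with close to 0.15, so its standard error is too large.

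Simulation of layout A, with power for a 1-SD difference:

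| ρ | Type I error, planned test | Power, planned test | Power, patient-block model |
|---|---|---|---|
| 0 | 5.0% | 71% | 69% |
| 0.2 | about 3% | 73% | 79% |
| 0.5 | about 1% | 77% | 93% |

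The block model holds type I error at about 5% in every row.

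**Layout B: shared unevenly** (operators on 4 'patients', 5 each; clinicians on 2 of those, 5 each).
- Net patient weights are 1/4 − 1/2 = −1/4 for two patients and +1/4 for the other two. The sum of squares is 4 × 1/16 = 0.25.
- True variance: 0.25ρ + 0.15(1 − ρ) = 0.15 + 0.10ρ, which is 0.16, 0.18 and 0.20 at ρ = 0.1, 0.3 and 0.5.
- The test's expected variance is 0.15 × (1 − 8ρ/28), which is 0.146, 0.137 and 0.129. The standard error is now too small.
- Simulated type I error: about 6%, 8% and 11%.

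**Layout C: disjoint 'patients'** (operators on 3, clinicians on 2 others). Type I error is 11%, 22% and 32% at ρ = 0.1, 0.3 and 0.5.

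**Layout D: one 'patient' for everyone, or a different one for every exam.** Type I error stays at about 5% in both.

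**Choice of matched analysis.** A one-sample test on per-patient mean differences is the obvious alternative to the block model, but it depends on the number of 'patients'. With 5 'patients' and ρ = 0.2 its power is 59%, against 74% for the planned test. With 2 'patients' it is 16% to 19%, against 70% to 79% (ρ from 0 to 0.3). The block model with 5 'patients' (4 operators and 2 clinicians each) gives 70% against 70% for the planned test at ρ = 0, and 79% against 73% at ρ = 0.2.

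**The case against.** The strongest case against is that nothing in the document breaks the match. C.1 states it, and C.5 uses the same term for the person scanned by clinicians as for the person scanned by operators in the first portion. This stands: the allocation is unspecified, not contrary to the match.

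A reader might infer that the plan carries a severely inflated false-positive rate, on the strength of figures such as the 11% to 32% of layout C. The document does not support that. In layout C no clinician image comes from an operator's 'patient', so it would breach C.1; it is not a property of the plan as written. Layout B is also imperfect by C.1, because half the operators have no clinician image of their 'patient', and its inflation is modest. One shared 'patient' would remove the problem for the first portion, although the plural in C.3 makes that reading less likely. A different 'patient' for every exam would leave the error rate intact but would itself give up the C.1 match.

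It is also fair that the size rests on ρ, for which the document gives no value. All 'patients' are healthy, and items such as probe and gain selection are technique items, so a share as high as 0.5 has no support in the text. At low shares the gain from blocking is small. Finally, this is described as an initial pilot of feasibility, which limits how much hangs on one test.

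What remains is that the stated comparator is not carried into either the schedule or the analysis, and that the schedule cannot be repaired once the scans are done.

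**Conclusion.** The concern holds as a gap between the comparator defined in C.1 and what C.3, C.5 and D specify. The consequence depends on a layout the plan leaves open:

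- **Balanced match:** no bias, but a conservative test that gives up about 6 points of power at ρ = 0.2 (79 − 73) and 16 points at ρ = 0.5 (93 − 77), for a 1-SD difference and 10 'patients'.
- **Uneven sharing:** type I error of about 6% to 11% for ρ from 0.1 to 0.5, in the one layout examined.
- **One shared 'patient', or a different one for every exam:** no inflation.

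All of these rest on assumed variance shares and layouts, and on a normal model for a bounded 0 to 6 score. The document does not support the stronger reading, that the plan abandons the match or that its contrast is necessarily biased. The point is worth acting on because the remedy is cheap and has to be in place before scanning starts.

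**What to change.** **Sections C.3 and C.5.** State the number of 'patients'. Schedule the scans so that each is scanned by operators and clinicians in the 2:1 enrolment ratio, whatever number is planned: for example 2 operators and 1 clinician on each of 10, or 4 and 2 on each of 5. If each clinician scans one 'patient', this is possible for up to 10.

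**Section D.** For the first-portion 'patient' exams, replace the unpaired t-test with a linear model of Final Score on group, with 'patient' as a block. Name which clinician exam, unguided or guided, enters the contrast. Do not use a test on per-patient mean differences, because it loses much power when 'patients' are few. With a single 'patient' the block model reduces to the planned t-test.

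**Self-exams.** Each is on the operator's own body, so no same-'patient' clinician image is planned. Analyse these scores separately and label the comparison as unmatched.

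**Cost.** A scheduling list, a short change to section D, and about 1 to 2 points of power if 'patients' do not differ (71% to 69% with 10 'patients', no visible loss with 5). No participants are added provided the planned number of 'patients' is kept. That number is not stated, so this cannot be confirmed from the document.

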## 2. Research Site

The study will be conducted at the Clinical Skills Center (CSC) at Stony Brook University School of Medicine (SBU)

## 3. Study sample

A convenience sample of 20 healthy volunteers will be recruited from the Stony Brook undergraduate campus to participate as 'operators' in the study. 'Patients' will be recruited from a pool of standardized patient models who regularly participate in activities in the CSC. 10 US-trained clinicians will be recruited from SBU.

## 4. Screening

Healthy volunteers will be recruited from the Stony Brook undergraduate campus. They will be screened for prior medical training, particularly regarding US technique. Those with any amount of US training and more than minimal medical/nursing training will be ineligible for participation.

## 5. Procedures

Volunteers will meet with study personnel in the CSC at SBU. Informed consent will be obtained from all groups ('operators', 'patients', 'clinicians'). A survey will be conducted to evaluate the subjects' prior experience in ultrasound. Subjects who qualify will continue to participate in the study.

The 'patient' will initially be evaluated by US by an expert and 'ideal' images will be captured and stored for later comparison against those obtained by 'operators'.

The 'operator' will be given an smart phone/table with video communication function and will be connected with the US 'expert', who will be located in a different room, physically and audibly out of range. For the first portion of the study, the 'expert' will instruct the 'operator' on how to conduct an US exam limited to the lung. Using the two-way video and audio communication through the video communication application, the expert will guide to the operator on how to utilize the US machine, where to place the probe, and how to capture and save images. The 'patient' will be instructed not to assist the 'operator' in any way. For the second portion of the study, the 'operator' will utilize the US machine to conduct a similarly limited lung exam on themselves, again with the assistance of the 'expert' but no other study personnel.

Finally, the 'clinicians' will carry out similarly limited lung exams on the 'patient', first without instruction from the 'expert' and then again under similar guidance as the previous portions of the study.

During all portions of the study, time to image capture will be measured by observing personnel. All captured images will be sent to expert reviewers at which time a quality score will be generated. Ultrasound experts will blindly evaluate images obtained from both untrained and trained groups. Using the 'Ultrasound Quality Scorecard', evaluators will assess the quality of the image obtained and the technique carried out to obtain the image. These quality and technique criteria include 'Discernable Lung Parenchyma', 'Presence of A-lines', 'Lack of Obstruction from Rib Shadowing', 'Correct Probe Selection', Correct Depth Setting', 'Correct Gain Selection'. For each criterion (both quality and technique), a binary 'Yes/No' score will be given. Total 'Yes' scores will be summed for each ultrasound exam (minimum 0, maximum 6), with the higher number of 'Yes' responses signifying a higher quality ultrasound exam. Each ultrasound exam will be scored by three separate experts, with the average of the three scores being reported as the 'Final Score'. Reviewers will be comprised of three experts in the field of US, all MDs who have received formal training in US and have at least 5 years of clinical US practice experience. Each captured image will be reviewed and scored by all three reviewers.

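### Clinician exams on a standardised patient are placed after the operator exam with no counterbalancing, so an order effect of unknown size and sign cannot be separated from the operator-clinician difference

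*Combined protocol and SAP*

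**What the plan says.** Section C.5 (Procedures) describes the exams in one order. An expert first scans the patient to obtain reference images. The operator then scans the patient under remote guidance: "For the first portion of the study, the 'expert' will instruct the 'operator' on how to conduct an US exam limited to the lung". Next comes the self-exam: "For the second portion of the study, the 'operator' will utilize the US machine to conduct a similarly limited lung exam on themselves". The clinicians come last: "Finally, the 'clinicians' will carry out similarly limited lung exams on the 'patient', first without instruction from the 'expert". Each clinician has a second exam too, and only that one is guided.

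Section C.1 (Rationale/overview) ties the two groups to a shared patient: "Images obtained by 'operators' will be compared against those obtained by US-trained clinicians (clinicians) captured from the same 'patient".

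Section C.3 (Study sample) gives 20 operators and 10 clinicians. Patients come from a "pool of standardized patient models who regularly participate in activities in the CSC"; their number is not stated, nor is the matching of operators and clinicians to patients.

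Section D (Statistical Analysis Plan) compares Final Scores between the groups with Student's t-test at the two-sided 5% level. It has no term for order or session, and it does not say which exam of each group enters the test.

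**The concern.** Read together, sections C.1 and C.5 mean that the clinician follows the operator on a given patient. Whatever changes between an earlier and a later scan of that patient then falls on one side of the comparison. Candidates include the patient's familiarity or fatigue, the guide's practice or fatigue, and machine settings left from the previous exam (probe selection, depth and gain are three of the six scored items, and no section asks for a reset).

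The study's main quantitative result is the difference between these two groups. If order affects scores, that difference is not purely one of training, and it could be too large or too small. Blinded image review protects against rater bias but not against something that happened when the image was acquired. Order can be balanced only before the data are collected.

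**Working it through.** **What the documents fix.** The plan gives no effect size, SD, power or order effect, so there is no figure of its own to reproduce. The inputs are n = 20 operators and n = 10 clinicians (section C.3), and Student's t-test at two-sided 5% (section D), hence df = 20 + 10 − 2 = 28 and a critical value of 2.048.

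**Why analysis cannot repair it.** Let Δ be the true clinician-minus-operator difference and δ the effect of being scanned later on the same patient. If every clinician exam is later, the expected observed difference is Δ + δ. One contrast cannot yield two unknowns, and adjustment needs some clinician exams that come first, of which the text provides none within a patient.

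**Which exams each route can reach.**
- Clinicians' first exam: unguided, so practice by the guide cannot affect it. Patient or machine effects could.
- Clinicians' second exam: guided, so guide practice is possible. It also always follows the clinician's own first exam.
- Operator's exam on the patient: already preceded by the expert's scan, so the patient is not being scanned for the first time.
- Later operators: if the guide improves with practice, they benefit too.

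**Sensitivity to an assumed δ.** In SD units the standard error of the difference is √(1/20 + 1/10) = 0.387. With Δ = 0, the noncentrality is δ/0.387, and the rejection probability is P(|T| > 2.048) for a noncentral t on 28 df:

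| Assumed δ (SD) | Noncentrality | Rejection rate |
|---|---|---|
| 0 | 0 | 5.0% |
| 0.10 | 0.26 | 5.7% |
| 0.25 | 0.65 | 9.6% |
| 0.50 | 1.29 | 23.9% |
| 0.75 | 1.94 | 46.4% |

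If instead Δ = 1.0 SD, power is 70% without an order effect; a shift of 0.25 SD moves it to 88% or 46%, depending on sign. All these rows assume that δ applies in full to every clinician exam in the test.

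**What alternation does.** If half of each group goes first and half later, each group mean carries δ/2, and the expected difference is (Δ + δ/2) − δ/2 = Δ. The price is added variance of δ²/4 per group: for δ = 0.5 SD the working SD becomes √(1 + 0.0625) = 1.03 times the original.

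**Whether order could then be tested.** The groups would split into about 10/10 operators and 5/5 clinicians. The contrast of the order effect between groups has a standard error of √(1/10 + 1/10 + 1/5 + 1/5) = 0.77 SD. With a t multiplier of about 2.06 (df = 26), the 95% half-width is about 1.6 SD. That is far too wide to detect shifts of 0.25 to 0.5 SD, so a description by order is all the data can support.

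**The case against.** A reader might infer something stronger: that accumulated practice by the guide and the patient favours the clinicians, that operators are therefore understated, and that group and order coincide throughout the study. The documents support none of this.

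- Guide practice cannot reach the clinicians' unguided exam, and section D does not say whether that exam or the guided one is used.
- The patients are experienced models, each scanned by the expert before any operator. The patient is told not to help: "The 'patient' will be instructed not to assist the 'operator' in any way". That instruction names only the operator, so whether it also covers the clinician exams is open.
- Fatigue or carried-over settings could act in either direction.
- The text does not show whether the closing step applies after all 20 operators or within each session. If sessions repeat by patient, operators and clinicians interleave in calendar time, and only the order within a patient is confounded.

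It can also be said that the assumed shifts are not evidence of an effect, that equality between untrained students and trained clinicians is an unlikely null, and that this is a non-randomised feasibility pilot whose groups differ in training by design. All of that stands. It makes order a secondary limitation and removes any claim about direction. It does not remove the core point: within a patient, as written, no clinician precedes an operator, and nothing in the plan balances or records this.

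**Conclusion.** The point holds in a limited form. Within a patient, group and order cannot be separated in the planned t-test, and the size and sign of any order effect are unknown. The rejection rates of about 10% (0.25 SD) and 24% (0.5 SD) rest on assumed shifts, no true group difference, and full application of the shift to the clinician exams analysed. They show how sensitive a 20 versus 10 comparison is, not that it is biased. The conclusion also rests on reading section C.5 literally as a sequence. If the sponsor intends another order, the text needs to say so. The change is worth making because it removes an avoidable confounder cheaply, not because a bias has been shown.

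**What to change.** In section C.5, replace the closing step with a rule that, on each patient, the order of operator and clinician sessions is alternated from a fixed list or randomised, with clinician sessions spread across the whole study. The rule needs the number of patients and the matching of the 20 operators and 10 clinicians to them, so state both.

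Record the session order for every exam. In section D, name which clinician exam and which operator exam enter the t-test, and report mean scores by group and order descriptively, without a formal test.

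Cost: slightly harder booking, since clinicians must attend across the study. No extra exam, staff or participant is needed. If the order cannot be changed, record it and state in the report that an order effect of unknown size and sign cannot be excluded.
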